8.3.3. Analysis of Secondary Endpoints

Observed values and change from baseline in the neurotransmitter CSF metabolites HVA, 5-HIAA, 3-OMD in CSF; brain ¹⁸F-DOPA PET; PDMS-2 total and subscale scores; Bayley-III cognitive and total language subscale scores; EQ-5D-Y scores; body weight; and AADC-specific symptoms will be summarized using descriptive statistics (count, mean, standard deviation, median, minimum, and maximum) or proportion as appropriate for each timepoint.

The number and percentage of subjects who achieve each motor milestone will be summarized by timepoint.

Oculogyric crisis diary data will be summarized by severity, frequency, and proportion and duration of time subjects experienced OGC during the study for selected timepoints, as appropriate.

Respiratory infection rate will be summarized over time.

TEAEs will be summarized as described in Section 8.3.2. The number of subjects who experience dyskinesia, number of dyskinesia episodes, median time to first episode, and summary statistics for duration of dyskinesia events will be provided.

Physical examination, vital signs, MRI, clinical laboratory values, T-cell, anti-AAV2 antibody values, and viral shedding will be summarized by visit, and shift table(s) will be provided if appropriate.

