2.1. Study Design

This is an open-label study in subjects with AADC deficiency. At minimum, 3 eligible pediatric subjects will be enrolled and receive eladocagene exuparvovec at 1.8×10^{11} vg via SmartFlow Magnetic Resonance (MR)-compatible ventricular cannula in a single operative session. Subjects will receive standard of care for their AADC deficiency during the study. Subjects will undergo Screening and a Baseline Visit before receiving eladocagene exuparvovec by intraputaminal infusion.

Subjects will return for regular visits during the course of the study. This study will have a Trial Phase, an Extension Phase, and a Long-Term Extension Phase. The length of the study, including the screening period, is 63 months (approximately 5 years).

The objectives of this study’s Trial Phase, Extension Phase, and Long-Term Extension Phase are as follows:

- The primary objectives of the Trial Phase are to assess the PD of eladocagene exuparvovec treatment by evaluation of HVA levels and to assess the safety of the SmartFlow MR-compatible-ventricular cannula for administering eladocagene exuparvovec to pediatric subjects with AADC deficiency. The secondary objectives of the Trial Phase are to further assess the PD of eladocagene exuparvovec in subjects with AADC deficiency using neurotransmitter metabolite assessment and PET analysis. The Trial Phase will be completed 8 weeks after administration of eladocagene exuparvovec.
- The Extension Phase is designed to capture additional clinical information for eladocagene exuparvovec through study evaluations, including changes in motor development, AADC-specific symptoms, and other PD measures. The Extension Phase will be completed at 48 weeks after administration of eladocagene exuparvovec.
- The Long-term Extension Phase is designed to capture long-term safety and efficacy data, for subjects treated with eladocagene exuparvovec, through Month 60.

A data safety monitoring board (DSMB) will conduct a formal review of safety data as outlined in the DSMB Charter. Review by DSMB will not be required to enroll successive subjects. The DSMB will monitor ongoing study results to ensure subject well-being, safety, and study integrity.

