2.4. Sample Size

The sample size is not based on statistical power consideration. A minimum of 3 subjects is planned to assess HVA levels at Week 8 and safety of the SmartFlow MR-compatible ventricular cannula for administering eladocagene exuparvovec to pediatric subjects.

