6.2.11. Annual Rate of Respiratory Infection/Pneumonia

For pneumonia and respiratory infection, preferred terms under INFECTION and INFESTATION SOC selected for summary include the following:

- Bronchiolitis
- Bronchitis
- Pneumonia
- Pneumonia Haemophilus
- Pneumonia Influenzal
- Pneumonia Mycoplasmal
- Pneumonia Viral
- Respiratory tract infection
- Stenotrophomonas infection

Infections will be summarized as:

- Annual rate for all subjects after receiving gene therapy
- Annual rates prior to and after achieving head control (PDMS-2 score=2) for subjects who gained head control
- Annual rate after gene therapy for subjects who did not achieve head control.

Annual rate will be calculated using total time of all subjects in the study for that year as denominator and the total number of episodes of infection/pneumonia during that year as numerator:

$$\text{Annual rate} = (\text{total number of episodes during that year}) / (\text{total time for that year})$$

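### The one denominator given for annual respiratory infection rates, the time of all subjects, does not match the episodes counted before, after or without head control

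*SAP*

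**What the plan says.** SAP 6.2.11 selects a set of respiratory preferred terms and lists three summaries:

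- The first covers everyone treated: "Annual rate for all subjects after receiving gene therapy".
- The second splits the time of those who reach the milestone into two periods: "Annual rates prior to and after achieving head control (PDMS-2 score=2) for subjects who gained head control".
- The third covers the remaining children: "Annual rate after gene therapy for subjects who did not achieve head control".

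It then defines the annual rate once. The denominator is described as follows: "Annual rate will be calculated using total time of all subjects in the study for that year as denominator". The numerator is "the total number of episodes of infection/pneumonia during that year as numerator". The displayed equation shortens the denominator to the total time for that year. No person-time is defined for any head-control group or period.

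The protocol supplies no rule to fall back on. Section 8.3.3 says only: "Respiratory infection rate will be summarized over time". SAP 4.4 records no change from the protocol analyses.

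**The concern.** A rate per child-year is interpretable only if the time in the denominator is the time during which an episode could have entered the numerator. A before-head-control episode can occur only while a future gainer is still without head control. An after episode can occur only once head control is present, and a never episode only in a non-gainer. The stated denominator also includes time from children and periods that cannot contribute to the numerator concerned.

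These rates are the SAP's only planned look at whether respiratory infection differs with head control. If the share of person-time enters each rate, a table could show a fall, a rise or no difference because of how many children gained head control and when.

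**Working it through.** The documents state no infection rate, so there is no figure to reproduce. The check is person-time arithmetic.

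**From the documents.** The formula is in SAP 6.2.11. Sample size, SAP 2.4: "A minimum of 3 subjects is planned to assess HVA levels at Week 8". Follow-up, SAP 2.1: "long-term safety and efficacy data, for subjects treated with eladocagene exuparvovec, through Month 60". PDMS-2 is scheduled at Baseline, Weeks 24 and 48, then Weeks 72, 96, 156, 208 and 260 (Protocol 7.1, Tables 1 to 3).

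**Assumed, not in the documents.** 10 children with complete follow-up, years of 52 weeks counted from dosing, and the numbers of gainers, times of gain and true rates shown below.

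**Formulas.** Let E be episodes and T child-years.

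- Reading A, subgroup episodes over the time of all subjects: E_sub / T_all = true rate × (T_sub / T_all).
- Reading B, subgroup episodes over the whole time in that year of the subjects named in the bullet.
- Reading C, neither half restricted: E_all / T_all, the same for every summary.
- Matched: E_sub / T_sub.

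**Case 1: 6 of 10 gain at Week 48, true rate 1.0 throughout, Year 1.** Before time is 6 × 48/52 = 5.54 child-years, after time 6 × 4/52 = 0.46, never time 4, all time 10. Episodes equal child-years.

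**Case 2: 8 of 10 gain at Week 24, true rates 2 before, 1 after, 2 never, Year 1.** Before time is 8 × 24/52 = 3.69 (7.38 episodes), after time 8 × 28/52 = 4.31 (4.31 episodes), never time 2 (4 episodes), all time 10.

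| Reading | Case 1: before / after / never | Case 2: before / after / never |
|---|---|---|
| A | 0.55 / 0.05 / 0.40 | 0.74 / 0.43 / 0.40 |
| B | 0.92 / 0.08 / 1.00 | 0.92 / 0.54 / 2.00 |
| C | 1.00 / 1.00 / 1.00 | 1.57 / 1.57 / 1.57 |
| Matched (truth) | 1.00 / 1.00 / 1.00 | 2.00 / 1.00 / 2.00 |

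In Case 1, readings A and B both show a 12-fold fall (48 weeks against 4) where nothing changed. In Case 2, the true never rate is twice the after rate. Reading A puts it slightly below the after rate. Reading B makes it nearly four times as high (2.00/0.54 = 3.7).

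**Later years of Case 1.** All gainers already have head control. Reading A gives after 6/10 = 0.60 and never 4/10 = 0.40 at equal risk. Reading B gives 1.00 for both. Reading B therefore fails in years when gainers spend time in both states.

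**Five years pooled, 8 of 10 gaining at Week 48, true rates 2/1/2.** The SAP formula is written per year, so this applies only if years are combined. Child-years are 7.38 before, 32.62 after and 10 never, 50 in all. Reading A gives 14.77/50 = 0.30, 32.62/50 = 0.65 and 20/50 = 0.40. A true halving after head control appears as roughly a doubling. Reading B (gainers' 40 child-years) gives 0.37 and 0.82, the same reversal.

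**Where the stated denominator is right.** The all-subject rate equals E_all / T_all and is correct on post-dose time. If nobody gains head control, T_never = T_all and the never rate is also correct.

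**The case against.** The strongest reply is that the text restricts neither half of the fraction, so it is one-sided to read the numerator as limited to a subgroup and the denominator as unlimited. The bullets already name who and when. The reference to all subjects may mean only that time is pooled rather than averaged child by child, and the displayed equation omits those words. Table shells are in a separate document (SAP 8) and could settle the matter. This stands to the extent that a wrong calculation is not certain. It does not clear the text. Limiting the denominator to the named subjects is reading B, which still fails for before and after. Limiting neither half is reading C, which removes the comparison. Matched rates require a further step, splitting gainers' time by state, that the section never mentions. SAP 6.2.10, just before it, does match its denominator to the interval for oculogyric crises.

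A reader might also infer that pre-dose time will be counted, because time in the study is not expressly post-dose. The documents largely answer this: Protocol 8.3 starts summaries at gene therapy administration, SAP 4.3 measures follow-up from dosing, and the first bullet says after gene therapy.

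Three further points stand. The magnitudes rest on assumptions, and the 12-fold figure comes from placing every gain at Week 48 and viewing only Year 1. The rate is not among the listed primary or secondary endpoints, and the study has no formal hypothesis testing (Protocol 8.1). All adverse events are listed by subject (SAP 7.1.1), so episodes can be checked.

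**Conclusion.** The point holds for the before, after and never head-control rates. The single stated denominator does not match the episodes those rates count, and nothing else in the documents supplies the missing person-time. Followed literally with subgroup episodes, each rate is the true rate times a share of person-time. In the assumed Case 1 that turns three equal rates of 1.0 into 0.55, 0.05 and 0.40. Other assumed numbers and times of gain change the size and can change the direction.

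Stronger statements are tempting but unsupported. Not every rate is affected, because the denominator suits the all-subject rate on post-dose time. The head-control rates do not reflect group size instead of risk; they reflect risk multiplied by share of time. They are not always too low: the never rate is right if nobody gains head control. Nor do the documents show that the reported table will be wrong, since a programmer may depart from the text and match the time. Severity is minor to moderate.

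**What to change.** Replace the denominator sentence in SAP 6.2.11 with a rule that, for each rate and year, episodes and post-dose person-time are both limited to the same subjects and the same head-control state:

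- All subjects: all post-dose time.
- Before: dosing to the head-control date, in subjects who gain it.
- After: head-control date to last follow-up.
- Never: dosing to last follow-up, in subjects without head control.

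Define the head-control date as the first PDMS-2 visit with a score of 2 on Stationary Item 10. The item needs naming because SAP Table 2 lists both partial (Item 5) and full (Item 10) head control. State that the true date lies between visits. Say how a child scoring 2 at baseline is handled, either as after from dosing or listed separately; the entry criteria require only inability to walk independently, so such a child is possible. Show episodes and child-years beside each rate.

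The cost is a short SAP text change and a little programming. Adverse event onset, dosing and visit dates are already collected. The remaining limitation is that head control is dated only to the visit, and visits are up to a year or so apart later in the study (Week 96 to Week 156 is 60 weeks).

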7. SAFETY ANALYSES

7.1. Adverse Events

All AEs (serious and non-serious) occurring after completion of the informed consent process up to required reporting period, regardless of relationship to study drug, will be included and classified by SOC and PT using the MedDRA version 26.0.

7.1.1. Treatment-emergent Adverse Events

A TEAE is any AE that occurs post study drug administration. If onset date is missing, the AE is considered as TEAE.

An overall summary of TEAEs will be provided for number and percentage of subjects experiencing the following:

- TEAE.
- TEAE related to gene therapy.
- TEAE related to surgical device.
- TEAE related to neurosurgical procedure.
- TEAE related to F-DOPA.
- TEAE by severity.
- TEAE leading to withdrawal.
- TEAE of special interest (TEAESI: dyskinesia and cerebrospinal fluid leakage)
- Treatment emergent SAE (TESAE)
- TESAE and reasons for SAE
- TESAE related to gene therapy.

In the overall summary of TEAEs table, besides tabulating the number and percentage of subjects, the total number of TEAE episodes will also be provided. If a subject has repeated episodes of a particular TEAE, all episodes will be counted in the summary table.

Summary of number and percentage of subjects experiencing a TEAE will be presented for the following:

- TEAE by PT in descending order of incidence
- TEAE by SOC and PT
- TEAE related to gene therapy by SOC and PT.
- TEAE related to surgical device by SOC and PT.
- TEAE related to neurosurgical procedure by SOC and PT.
- TEAE related to F-DOPA by SOC and PT.
- TEAE by SOC, PT, and severity.

- TEAE leading to withdrawal by SOC and PT.
- TEAESI by SOC and PT.
- TESAE by SOC and PT
- TESAE related to gene therapy by SOC and PT

In the summary tables listed above, the percentage of subjects with TEAEs will be calculated by dividing the number of subjects who have experienced the event by the total number of subjects in the safety set. If a subject has repeated episodes of a particular TEAE, only the most severe episode, or the episode with the strongest causal relationship to study drug, will be counted in the summary tables.

A subject with more than one type of TEAE in a particular SOC will be counted only once in the total of subjects experiencing TEAEs in that particular SOC. Since a subject could have more than one type of TEAE within a particular SOC, the sum of subjects experiencing different TEAEs within the SOC could appear larger than the total number of subjects experiencing TEAEs in that SOC. Similarly, a subject who has experienced a TEAE in more than one SOC will be counted only once in the total number of subjects experiencing AEs in all SOCs.

In addition, a summary of dyskinesia will be presented to show number of subjects experienced treatment emergent dyskinesia, total number of events categorized by event severity, median time to first episode after gene therapy, and summary statistics of duration of dyskinesia.

All occurrences of all AEs will be listed for each subject.

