Statistical Methods:	
Summaries and descriptive statistics will be provided for PD, safety, and efficacy variables from time of gene therapy administration until the end of follow-up. If needed, summaries will be provided for PD, efficacy, and safety variables at a timepoint that matches the agreement with the health authority.
 
Observed values and change from baseline in HVA at Week 8 will be summarized using descriptive statistics (count, mean, standard deviation, median, minimum, and maximum) for each timepoint
 
Observed values and change from baseline in the neurotransmitter CSF metabolites HVA, 5-HIAA, 3-OMD in CSF; brain ¹⁸F-DOPA PET; PDMS-2 total and subscale scores; Bayley-III cognitive and total language subscale scores; EQ-5D-Y scores; body weight; and AADC-specific symptoms will be summarized using descriptive statistics (count, mean, standard deviation, median, minimum, and maximum) or proportion as appropriate for each timepoint.
 
The number and percentage of subjects who achieve each motor milestone will be summarized by timepoint.
 
Oculogyric crisis diary data will be summarized by severity, frequency, and proportion and duration of time subjects experienced oculogyric crises (OGC) during the study for selected timepoints, as appropriate.
 
Respiratory infection rate will be summarized over time.
 
The primary safety analysis will focus on TEAEs that are defined as AEs with a start date after or worsen after receiving eladocagene exuparvovec.
 
The time of gene therapy administration will be the start time of the first infusion. All AEs reported will be coded using MedDRA. The

	
number and proportion of subjects reporting TEAE will be summarized by System Organ Class (SOC) and by Preferred Term (PT) within SOC. Summaries will also be provided for each severity grade, relationship to the cannula device, to gene therapy, and to neurosurgical procedure, and for AEs of special interest.
 
The number of subjects who experience dyskinesia, number of dyskinesia episodes, median time to first episode, and summary statistics for duration of dyskinesia events will be provided.
 
Physical examination, vital signs, MRI, clinical laboratory values, T-cell, anti-AAV2 antibody values, and viral shedding will be summarized by visit, and shift table(s) will be provided if appropriate.

--	---

PROTOCOL IDENTIFIERS AND STUDY PERSONNEL

Project Code	PTC-AADC
Therapeutic Area	Gene therapy

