7.5.6. Grading of Severity of Adverse Events

The severity of AE will be graded using the Common Terminology Criteria for Adverse Events (CTCAE) Version 5.0. For each episode, the highest severity grade attained should be reported.

If a CTCAE criterion does not exist, the investigator should use the grade or adjectives: Grade 1 (mild), Grade 2 (moderate), Grade 3 (severe), Grade 4 (life-threatening), or Grade 5 (fatal) to describe the maximum intensity of the AE. For purposes of consistency with the CTCAE, these intensity grades are defined in [Table 5](#).

Table 5: Grading of Adverse Event Severity Grade

Grade	Adjective	Description
1	Mild	Sign or symptom is present, but it is easily tolerated, is not expected to have a clinically significant effect on the subject's overall health and well-being, does not interfere with the subject's usual function, and is not likely to require medical attention
2	Moderate	Sign or symptom causes interference with usual activity or affects clinical status, and may require medical intervention
3	Severe	Sign or symptom is incapacitating or significantly affects clinical status and likely requires medical intervention and/or close follow-up
4	Life-threatening	Sign or symptom results in a potential threat to life
5	Fatal	Sign or symptom results in death

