7.5.8. Adverse Event Reporting Period

Investigator site reporting requirements for AEs are summarized in [Table 6](#).

Table 6: Investigator Site Requirements for Reporting Adverse Events

Event	Recorded on the eCRF	Reported to PTC Pharmacovigilance Within 24 Hours of Awareness
Serious AE	All	All
Nonserious AE	All	None
AESIs	All	All
Other, eg, exposure to the gene therapy during pregnancy or breastfeeding, and occupational exposure	All (regardless of whether associated with an AE), except occupational exposure	All (regardless of whether associated with an AE)

Abbreviations: AE, adverse event; AESI, adverse event of special interest; eCRF, electronic case report form

The first day of AE reporting will coincide with the date of signing of informed consent and including a minimum of 30 calendar days after the Final Study Visit (Month 60), except as

described in Section 7.5.4. In addition, SAEs occurring in a subject after the study period should be reported to the sponsor if the investigator becomes aware of them.

The medical monitor will review all AEs and SAEs as they are reported from the site. The DSMB will conduct a review of safety data as outlined in the DSMB charter. The DSMB will monitor ongoing safety data to ensure subject well-being, safety, and study integrity.

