8.3.2.2. Primary Safety Analysis

The primary safety analysis will focus on TEAEs that are defined as AEs with a start date after or worsen after receiving eladocagene exuparvovec.

The time of gene therapy administration will be the start time of the first infusion. All AEs reported will be coded using MedDRA. The number and proportion of subjects reporting TEAE will be summarized by System Organ Class (SOC) and by Preferred Term (PT) within SOC. Summaries will also be provided for each severity grade, relationship to cannula device, to gene therapy, and to neurosurgical procedure, and AEs of special interest.

Serious Adverse Events will be summarized using SOC and PT.

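### SAP 7.1.1 leaves the protocol's worsening limb out of the TEAE definition and declares no change, so an AE that starts between consent and the first infusion and then worsens drops out of the primary safety summaries

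*SAP*

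**What the plan says.** Protocol 8.3.2.2 sets the rule on which the main safety tables rest, counting as treatment-emergent all "AEs with a start date after or worsen after receiving eladocagene exuparvovec". In the synopsis, the statistical methods part gives the same two limbs. Protocol 8.3.2.2 also fixes the cut-point: "The time of gene therapy administration will be the start time of the first infusion".

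SAP 7.1.1 has one limb, "A TEAE is any AE that occurs post study drug administration", and one supplementary rule, "If onset date is missing, the AE is considered as TEAE". No rule on worsening appears anywhere in the SAP, and the SAP does not repeat the first-infusion cut-point. SAP 4.4, which exists to record departures from the protocol's analyses, reports none.

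AEs are collected before dosing. Protocol 7.5.8 says "The first day of AE reporting will coincide with the date of signing of informed consent", and SAP 7.1 likewise takes in AEs from informed consent onwards. On severity, Protocol 7.5.6 says "For each episode, the highest severity grade attained should be reported". The items that Protocol 7.5.4 requires for each AE include onset and resolution dates, but no date of worsening.

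**The concern.** The AE summaries in SAP 7.1.1 (overall, by severity, by relationship to gene therapy, device and neurosurgical procedure, leading to withdrawal, and serious) are all restricted to treatment-emergent events. The definition therefore decides what the primary safety analysis can show. Dropping a limb can only remove events; it cannot add any.

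There is no fallback table for serious events. Protocol 8.3.2.2 asks for SAEs by SOC and PT, whereas the SAP tabulates only treatment-emergent SAEs. A pre-dose AE that becomes serious after dosing would then be in neither kind of table.

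The worsening limb matters most near the operation. The cut-point is the first infusion, so anaesthesia and the surgical steps before it fall on the pre-dose side; note m of protocol Table 1, for example, has CSF drawn during surgery before dosing. An event that begins in that interval and progresses after the infusion bears directly on the primary safety endpoint, AEs associated with surgical administration through the cannula. Whether the SAP would lose it is unclear, because the SAP has no rule for events on the day of dosing and Protocol 7.5.4 lists an onset date but no onset time.

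**Working it through.** No figure in the plan depends on this point, so there is nothing to reproduce. The check is to pass each type of AE record through both rules.

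**Inputs.** Protocol rule: start after dosing, or worsening after dosing (Protocol 8.3.2.2, synopsis). SAP rule: occurrence after dosing, with missing onset counted as treatment-emergent (SAP 7.1.1). Minimum enrolment: 3 subjects (Protocol 8.1, SAP 2.4).

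| AE record | Protocol rule | SAP rule |
|---|---|---|
| Onset after first infusion | TEAE | TEAE |
| Onset before, worsens after | TEAE | not a TEAE |
| Onset before, does not worsen | not a TEAE | not a TEAE |
| Onset missing | no rule given | TEAE |

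The second row is the conflict. The fourth is an addition by the SAP, not a contradiction.

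**Pre-dose window.** Table 1 of the protocol schedules Screening from Week -10 to Week -2, and dosing on Day 1. Its note b allows up to 9 weeks from Screening to Baseline, and Baseline is at Week -1: 9 + 1 = 10 weeks. That is the upper limit if the visit windows are kept and reporting starts at consent. The AE row of Table 1 is blank at Screening and first marked at Baseline, which would leave about 1 week.

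**Effect on one table row.** If one affected child has no other TEAE in that row, the row changes by 100/N percentage points:

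- N = 3 (planned minimum): 100/3 = 33.3 points, that is 1/3 against 0/3.
- N = 5 (assumed): 100/5 = 20.0 points.
- N = 8 (assumed): 100/8 = 12.5 points.

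If the child already has another TEAE in the row, the count of subjects does not change, though the severity or relatedness shown for that child may.

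**Frequency.** The documents give no count or rate of pre-dose AEs, so the expected number of affected events cannot be calculated.

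**The case against.** One could argue that the SAP's word for occurrence is loose enough to include worsening. The sentence after it refers to onset date, which suggests that classification runs on onset. At best the SAP is ambiguous about the primary safety analysis.

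A stronger objection is that most of the clinically expected worsening is not lost at all. A reader might infer that aggravation of chronic dystonia or feeding difficulty after surgery would vanish from the tables. The documents do not support that. Protocol 7.5.2.1 makes worsening of a pre-existing illness an AE in its own right, while the stable condition is only noted at screening. Such an event counts under the SAP too, provided its onset is recorded as the date of worsening; the documents do not state that convention. Clinically active infection is an exclusion criterion and eligibility is rechecked at Baseline, which narrows the class further. This objection stands and limits the point to AEs whose recorded onset lies between consent and first infusion.

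It is also fair to say that other outputs limit the loss. SAP 7.1.1 lists every occurrence of every AE by subject, and such a listing is readable in full at 3 subjects. AADC-specific symptoms are tabulated by severity and visit (SAP 6.2.9), brain MRI has a shift table (SAP 7.2.7), and the DSMB evaluates all AEs (Protocol 7.5.12). The safety analysis is descriptive, with no decision rule on a TEAE percentage. All of this stands, but none of it puts the event back into the TEAE summaries that the protocol names as the focus of the primary safety analysis.

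Finally, a reader might infer from Protocol 7.5.4 and 7.5.6 that a worsening AE is necessarily a single record whose timing cannot be recovered. The text points that way, but the eCRF and its completion instructions are not among the documents and the protocol does not define an episode. This is something to confirm, not an established defect.

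**Conclusion.** The discrepancy is real and undeclared. Followed as written, the SAP drops from its TEAE, severity, relatedness and TESAE summaries any AE with recorded onset between consent and the start of the first infusion that worsens afterwards, and the error runs only towards fewer events. The AESI tables are less exposed, since the two events the SAP names there, dyskinesia and CSF leakage, are described in Protocol 7.5.3 as consequences of treatment and are unlikely to have begun weeks before it.

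The number of affected events is unknown. The 33-point change applies at N = 3, for one affected child with no other TEAE in the row, and shrinks as enrolment grows. The conclusion assumes that the SAP classifies by onset, as its missing-date rule suggests, and that a worsening event keeps its pre-dose onset date. It does not depend on the full 10-week window: any AE recorded from Baseline onwards is enough.

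**What to change.** 1. In SAP 7.1.1, define a TEAE as an AE with onset after the start of the first infusion, or with earlier onset and an increase in severity after it. Keep the existing rule for missing onset. If the narrower definition is intended, declare and justify it in SAP 4.4 instead.
2. Confirm in the eCRF completion instructions that an increase in grade after the infusion is captured with its date, for example by opening a new record. Without this, the restored limb may be hard to apply, because only the highest grade per episode is requested and no worsening date is listed.
3. Where an AE with pre-infusion onset is known to have worsened but the date of worsening is missing, count it as a TEAE. Do not extend this to pre-dose AEs that never worsened or that resolved before the infusion; they have no worsening date either, and counting them would inflate the tables.

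The cost is one sentence in the SAP, a short rule for missing dates and one eCRF instruction. A few more events may be counted as treatment-emergent, so the safety profile may look slightly less favourable.
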